1.1. Objectives, Endpoints, and Estimands

Objectives	Endpoints
Primary	
To assess the effect of alternative donanemab dosing regimens versus the standard donanemab dosing regimen on ARIA-E frequency	Proportion of participants with any occurrence of ARIA-E by Week 24
Secondary	
To assess the effect of alternative donanemab dosing regimens versus the standard donanemab dosing regimen on ARIA-E frequency	Proportion of participants with any occurrence of ARIA-E by Week 52
To assess the effect of alternative donanemab dosing regimens versus standard donanemab dosing regimen on brain amyloid deposition	Change from baseline in brain amyloid plaque deposition as measured by amyloid PET scan through Week 24 Week 52 Week 76
To evaluate the effect of alternative donanemab dosing regimens on ARIA events	 Proportion of participants with any occurrence of ARIA-H by Week 24 Week 52 ARIA-E and ARIA-H by severity

To assess peripheral PK and presence of anti-donanemab antibodies	 Serum PK of donanemab ADAs against donanemab, including TE-ADAs and neutralizing antibodies
Tertiary/Exploratory	
To explore characteristics that predict risk of ARIA-E and ARIA-H	 Association between exploratory MRI imaging sequences and the occurrence and severity of ARIA events Association between blood-based biomarkers and the frequency and severity of ARIA events NfL pTau Aß levels (40 and 42) GFAP sTREM2 hsCRP
To evaluate the effect of alternative donanemab dosing regimens on IRR	IRR events frequency and severity

Abbreviations: Aß = amyloid-beta peptide; ADA = antidrug antibody; ARIA = amyloid-related imaging abnormalities; GFAP = glial fibrillary acidic protein; hsCRP = high-sensitivity C-reactive protein; IRR = infusion related reaction; NfL = neurofilament light chain; PET = positron emission tomography; PK = pharmacokinetic; pTau = phosphorylated tau; sTREM2=soluble triggering receptor expressed on myeloid cells 2; TE = treatment-emergent.

Primary estimand

The primary clinical question of interest is:

What is the frequency of ARIA-E events at Week 24 in participants with early symptomatic AD treated with an alternative donanemab dosing regimen and is there a difference compared to the standard donanemab dosing regimen, regardless of discontinuation or interruption of donanemab dosing for any reason and regardless of change in background AD medication?

The estimand is described by the following attributes:

- Population Participants with early symptomatic AD
- Endpoint Occurrence of ARIA-E by Week 24
- Treatment condition 4 randomized treatment arms of donanemab with varying dosing schemes

- Population-level summary The relative difference in proportion of participants with any
 occurrence ARIA-E events in the alternative donanemab regimen compared to the
 standard donanemab regimen.
- Intercurrent events "Discontinuation or interruption of donanemab dosing for any reason" and "change in background AD medication." No other intercurrent events are considered.

The estimand strategy is treatment policy. Data will be collected and analyzed regardless of post randomization events in the first 24 weeks of the trial. This strategy will be implemented by a Bayesian logistic regression model. Rationale for this estimand is to evaluate the effect of alternative donanemab dosing regimens versus the standard donanemab dosing regimen on ARIA-E rate, as the study primary objective stated.

1.2. Study Design

Study AACQ is a multicenter, randomized, double-blind, Phase 3b study of donanemab in participants with early symptomatic AD. There will be 4 treatment arms in this study. All participants will receive a dosing regimen that includes donanemab, but at different dose levels and frequency of dosing. There is no placebo arm in this study, however, placebo is given at specific visits to preserve the blind for different dosing regimens.

The following table describes the planned dosing regimens for the first 16 weeks. At or after Week 16, all participants are targeted to receive 1400 mg of donanemab monthly until they meet the dose stopping criteria or until the end of the study. Before Week 16, total amount of donanemab dosage equals 3500 mg among all 4 treatment arms.

Visit Number	2	3	4	5	6	7	8	9	10
Study Week	0	2	4	6	8	10	12	14	16
Treatment Arm					Dose (mg)			
1-standard regimen	700	PBO	700	PBO	700	PBO	1400	PBO	1400
2-dose skipping	700	PBO	PBO	PBO	1400	PBO	1400	PBO	1400
3-titration	350	PBO	700	PBO	1050	PBO	1400	PBO	1400
4-Cmax	350	350	350	350	350	350	700	700	1400

Abbreviations: Cmax = concentration maximum; PBO = placebo.

If a participant meets amyloid plaque reduction criteria defined by the sponsor, as measured by amyloid PET scan, at Visit 12 (Week 24) or Visit 19 (Week 52), the participant will discontinue donanemab and stay in the study for the remaining study visits.

AACQ study duration will be up to approximately 91 weeks, which includes a screening period (7 weeks), a double-blind treatment period (76 weeks), and a follow-up visit that occurs 8 weeks after the last dose of study intervention.

2. Statistical Hypotheses

Suppose p_1 , p_2 , p_3 , and p_4 are ARIA-E rates at Week 24 in the standard dosing arm, the dosing skipping arm, the titration arm and the Cmax arm, respectively. There are 3 parameters associated with the primary objective of Study AACQ: 1) the relative risk reduction in ARIA-E in the 2nd treatment arm (dose skipping regimen) versus the 1st treatment arm (standard dosing regimen) at Week 24, denoted by $RD_{21} = \frac{p_1 - p_2}{p_1} = 1 - \frac{p_2}{p_1}$, where $\frac{p_2}{p_1}$ represents a relative risk between the 2nd treatment arm and 1st treatment arm. A positive relative risk reduction means the relative risk is smaller than 1; 2) the relative risk reduction in ARIA-E in the 3nd treatment arm (titration regimen) versus the 1st treatment arm at Week 24, denoted by $RD_{31} = 1 - \frac{p_3}{p_1}$, where $\frac{p_3}{p_1}$ represents a relative risk between the 3rd treatment arm and 1st treatment arm; 3) the relative risk reduction in ARIA-E in the 4th treatment arm (Cmax regimen) versus the 1st treatment arm at Week 24, denoted by $RD_{41} = 1 - \frac{p_4}{p_1}$, where $\frac{p_4}{p_1}$ represents a relative risk between the 4th treatment arm and 1st treatment arm.

A relative risk reduction in ARIA-E greater than 0 (which implies relative risk smaller than 1) favors alternative treatment arm. The posterior probability of obtaining at least 20% relative risk reduction of ARIA-E comparing the alternative dosing regimen versus the standard dosing regimen by Week 24 is considered as a positive primary outcome. Bayesian logistic regression will yield 3 posterior distributions of RD_{21} , RD_{31} , and RD_{41} . Afterwards, following 3 posterior probabilities will be derived:

$$Pr(RD_{21} \ge 0.2 \mid 24$$
-week ARIA-E data); (1)

$$Pr(RD_{31} \ge 0.2 \mid 24\text{-week ARIA-E data});$$
 (2)

$$Pr(RD_{41} \ge 0.2 \mid 24\text{-week ARIA-E data}).$$
 (3)

Conditional on 24-week ARIA-E data, the computed posterior probability from (1), (2), or (3) will evaluate how likely it is to achieve at least 20% relative risk reduction in ARIA-E comparing the alternative treatment arm with the standard one. A posterior probability >80% will lead to a conclusion that at least 1 alternative dosing regimen reduces ARIA-E risk by at least 20% compared to standard dosing regimen.

2.1. Multiplicity Adjustment

Adjustments for multiplicity will not be applicable for this study.

3. Analysis Sets

For the purposes of analysis, the following analysis sets are defined below:

Participant Analysis Set	Description
Entered	All participants who sign the informed consent form.
Randomized	All participants who are randomly assigned to 1 of 4 treatment arms.
Safety analysis set	All randomized participants who are exposed to at least 1 dose of donanemab. This safety analysis set is used to analyze all the safety endpoints during the treatment period plus safety follow-up.
Evaluable efficacy analysis set	Randomized participants with baseline and at least 1 post-baseline measure of interest.
Per-Protocol analysis set	All subjects in the Randomized Analysis Set population who also:
	 signed the inform consent form had no violations of inclusion/exclusion criteria
	 had no study dosing algorithm violation (such as if subjects randomized to treatment A were given treatment B or subjects randomized to treatment A never received the assigned study drug) adhered to the dosing titration scheme required in the first 16 weeks of this study
	were not considered non-compliant with regard to study drug

4. Statistical Analyses

4.1. General Considerations

As 4 donanemab dosing regimens including the standard one are available for Study AACQ, any safety or biomarker analysis will involve 3 comparisons: 1) dose skipping vs. standard dosing; 2) titration vs. standard dosing; 3) Cmax (concentration maximum) vs. standard dosing.

Safety analyses will include subjects who are randomized to study treatment and who take at least 1 dose of treatment. Subjects will be analyzed according to the treatment arm to which they were assigned.

Unless otherwise specified, analyses for ARIA events are based on MRI findings or AE (adverse events) reporting. ARIA safety analyses will cover both ARIA-E and ARIA-H events by Week 24 as well as by Week 52. Bayesian logistic regression method is proposed to obtain a posterior distribution regarding relative risk reduction in ARIA-E or ARIA-H at Week 24 or 52 for each of 3 comparisons mentioned above. The details of logistic regression model, prior elicitation, and computation for the posterior distribution will be presented in Section 4.3.2. From each derived posterior distribution of RD_{21} , RD_{31} , and RD_{41} , summary statistics will be reported which include posterior mean, posterior median, posterior mode, a 2-sided equal-tailed 95% posterior interval (often cited as credible interval in Bayesian literature), and a posterior probability of achieving a minimum of 20% relative risk reduction in ARIA-E.

Frequentist methods will be used for the rest of the study objectives. All frequentist tests will be conducted at a 2-sided alpha level of 0.05; 2-sided confidence intervals (CIs) will be displayed with a 95% confidence level.

Unless otherwise noted baseline is defined as the last measurement prior to dosing. When change from baseline is assessed, subjects will only contribute to the analysis if both a baseline and a post-baseline measurement are available. Endpoint is the last non-missing post-baseline measurement within the time period for the given analysis.

To allow for evaluation of the primary and secondary hypotheses at 24 and 52 weeks, database locks and the assessments of corresponding primary and secondary objectives are expected to occur after all participants in the Safety Analysis Set have had the opportunity to complete visits 12 and 19 including PET and MRI assessments. The sponsor may choose not to have a separate database lock after visit 19 and wait to perform the analyses for 52-week data until the final database lock.

Any change to the data analysis methods described in the protocol will require an amendment ONLY if it changes a principal feature of the protocol. Any other change to the data analysis methods described in the protocol and the justification for making the change will be described within this SAP and/or clinical study report (CSR).

4.2. Participant Disposition

Reason(s) for treatment and study discontinuation will be summarized by treatment arm for all randomized participants. The percentage of participants discontinuing from each treatment arm

will be compared between arms using Fisher's exact test. The comparisons will be done for the overall percentage of participants who discontinue and for select specific reasons for discontinuation.

4.3. Primary Endpoint Analysis

4.3.1. **Definition of endpoint(s)**

The primary endpoint will be the occurrence of ARIA-E as diagnosed by the scheduled or unscheduled MRIs or reported as treatment-emergent cluster up to and including Visit 12 (Week 24). The scheduled MRIs for the primary endpoint occur at weeks 4, 12, and 24.

4.3.2. Main analytical approach

The number of ARIA-E events and the percentage of participants by treatment arm with any occurrence of ARIA-E events will be tabulated. The percentage of any occurrence of ARIA-E events is equivalent to ARIA-E incidence proportion. The primary analysis will use a Bayesian logistic regression model to estimate relative risk reduction in ARIA-E between alternative donanemab dosing regimen and standard donanemab dosing regimen given ARIA-E data up to Week 24.

The logistic regression model will include categorical effects of treatment arm, APOE e4 genotype, baseline presence of microhemorrhage, baseline presence of superficial siderosis, and baseline amyloid level. Treatment arm is a multinomial variable with 4 levels. APOE e4 genotype status has 3 levels: heterozygous carrier, homozygous carrier, and non-carrier. As participants with ≤4 microhemorrhages at baseline are eligible to enroll into this study, the model needs to adjust for baseline presence of microhemorrhage which is a binary predictor. The proposed model will also assess the impact of baseline presence of superficial siderosis because the study allows enrollment of eligible subjects with 1 area of cortical superficial siderosis. Baseline amyloid values are divided into terciles.

An integral part of Bayesian analysis is the formulation of prior distributions for regression coefficients. A diffuse prior will be assigned to all slope parameters to reflect the impact of the alternative dose regime and the effect of baseline covariates solely based on the data collected from the study. For the intercept parameter, a mixture prior will be using information on ARIA-E rates of the standard donanemab dosing regimen by 24 weeks from AACI – Addendum 9 study. The mixture prior will have a diffuse and an informative component. However, the informative component will have much less variability than the diffuse component. Both prior means are equal to log odds of the ARIA-E incidence in AACI-Addendum 9 study at Week 24. One normal prior has much less variability compared to another normal prior that is relatively flat. 50% weight will be assigned to each component of the mixture a priori.

Through an iterative MCMC (Markov chain Monte Carlo) sampling method, a posterior distribution of ARIA-E incidence in Arm 1 (p_1) , Arm 2 (p_2) , Arm 3 (p_2) , or Arm 4 (p_4) at Week 24 will be simulated knowing the likelihood function of the logistic regression and prior density of individual regression coefficient. Afterwards, a posterior distribution of relative risk reduction in ARIA-E such as RD_{21} , RD_{31} , or RD_{41} as defined in Section 2 will be generated as well.

Posterior summary statistics, like posterior mean, posterior median, 2-sided equal-tailed 95% of posterior interval of RD_{21} , RD_{31} , or RD_{41} may be reported. The posterior probability of RD_{21} , RD_{31} , or RD_{41} being no smaller than 20% will be presented as well. The Bayesian logistic regression model can be implemented via both MCMC procedure in SAS and rjags package in R.

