# **6.3.** Assignment to Study Intervention

#### Randomization

All participants will be centrally assigned to randomized study intervention using an IWRS. Before the study is initiated, the login information and directions for the IWRS will be provided to each site.

Participants will be randomly assigned to 1 of 4 treatment groups in a 1:1:1:1 ratio.

Participants will be stratified at baseline by amyloid PET scan results ( $\geq$ 24.1 and <54 centiloids;  $\geq$ 54 and <79 centiloids;  $\geq$ 79 and <107 centiloids;  $\geq$ 107 centiloids) and *APOE* genotype (heterozygous carrier, homozygous carrier, and noncarrier).

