# 9.3.2. Primary Endpoint Analysis

Unless otherwise specified in the SAP, the primary endpoint will be based on the ARIA-E events as diagnosed by the scheduled or unscheduled MRIs up to and including Visit 12.

The primary analysis will use a Bayesian logistic regression model to estimate and compare the relative reduction in ARIA-E rates by Week 24 for the alternative donanemab regimens versus the standard donanemab regimen. The logistic regression model will include the fixed effects for treatment, ApoE e4 status, and baseline amyloid level. The treatment effects will be presented in terms of the estimated odds ratios and relative reduction in ARIA-E rates by Week 24 for the alternative regimens relative to the standard regimen. The Bayesian CSF for the primary analysis will be defined in the SAP, and the 95% credible intervals will be provided for the key parameters of interest.

The primary analysis model will have the ability to leverage information on the ARIA-E rate of the standard donanemab regimen by Week 24 through the construction of an informative prior using historical data. A mixture prior specification will be used to dynamically incorporate information based on the similarity in the ARIA-E rates of the standard regimen by Week 24 compared to the historical data. The details of the analysis model along with the prior information and the details about the sources of historical data will be outlined in the SAP.

A secondary analysis using the Bayesian logistic regression model for the primary endpoint will be fit using data from Study AACQ only, that is, in the absence of using historical data on the ARIA-E rate by Week 24.

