4.6.2.	Adverse events	
4.6.3.	Clinical laboratory evaluation	23
4.6.4.	Vital signs and other physical findings	24
4.6.5.	Columbia-Suicide Severity Rating Scale	25
4.6.6.	Amyloid-Related Imaging Abnormalities (ARIA)	26
4.6.7.	Hypersensitivity/Infusion Related Reactions	27
4.6.8.	Safety MRIs	27
4.7.	Interim Analysis	28
5.	Sample Size Determination	29
6.	Supporting Documentation	30
6.1.	Appendix 1: Demographic and Baseline Characteristics	
6.2.	Appendix 2: Treatment Compliance	30

LY3002813

7.	References	32
6.5.	Appendix 5: Handling Missing Data from Participant Dropouts	31
6.4.	Appendix 4: Multicenter Studies	31
6.3.	Appendix 3: Concomitant Therapy	30

Version history

This SAP for Study I5T-MC-AACQ is based on the protocol dated 28OCT2022.

SAP Version	Approval Date	Change	Rationale
1.0	27APR2023	Not Applicable	Original version
2.0		• Change reduction in proportion to difference in proportion in Section 1.1.	• Such a change is more aligned with the language in primary objective.
2.0		• In Section 2, define p_1 - p_4 .	Needs such definitions.
2.0		• Introduce relative risk in addition to relative risk reduction.	• Highlight the fact a relative risk <1 implies a positive relative risk reduction.
2.0		• Add posterior probability being more than 0.8 to be considered as a significant result.	• SAP (V1.0) did not mention benchmark value of posterior probability to be considered significant.
2.0		Replace amyloid PET analysis set with evaluable efficacy analysis set.	• Current EES includes any randomized patient with baseline and at least 1 post-baseline measure of interest.
2.0		Add per-protocol analysis set.	• SAP (V1.0) did not include this analysis set.
2.0		• For the Bayesian model specification, baseline PET values are divided into tertiles.	• In previous SAP, baseline PET in centiloids was a continuous covariate in the logistic regression model
2.0		• Change threshold value to 0.8.	• SAP (V1.0) did not cite this number correctly.
2.0		• Analysis of PET data at 24, 52, and 76 weeks.	• SAP (V1.0) used around 24, 52, and 74 weeks.
2.0		Minor editing.	• Increase readability.

2.0	Add PET analysis based on per-protocol analysis set.	• This is a sensitivity analysis for PET results using randomized population.
2.0	Add an alternative method of CMH test to analyze severity of ARIA- E and ARIA-H.	• Previously, only Fisher's exact test was proposed. CMH test can treat severity as an ordinal measurement.

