4.4.2. Amyloid plaque deposit

Participants' brain amyloid deposition will be measured by amyloid PET imaging at visits of screening, 24, 52 and 76 weeks. The frequency and percentage of subjects who achieved amyloid PET clearance (< 24.1 centiloids) in AACQ will be reported. And the count and percentage of subjects who meet dose stopping criteria either due to amyloid < 11 centiloids on one occasion or amyloid between 11 and 25 centiloids on two consecutive measurements will be presented at Week 24, Week 52, or Week 76.

The change from baseline to the post-baseline visit of the amyloid imaging centiloid will be evaluated using a MMRM (mixed model repeated measures) model which includes the fixed effects of treatment arm, time, treatment arm-by-time interaction, baseline age, baseline amyloid level, and baseline amyloid-by-time interaction. Treatment arm, time, as well as treatment arm-by-time interaction are the categorical effects and baseline age, baseline amyloid level, as well as baseline amyloid-by-time interaction are continuous effects. The within-patient covariance matrix of the MMRM is an unstructured one with no assumption made about the variances and covariances. If the unstructured covariance structure matrix results in a lack of convergence, the following tests will be used in sequence:

- heterogeneous Toeplitz covariance structure
- heterogeneous autoregressive covariance structure
- heterogeneous compound symmetry covariance structure
- compound symmetry covariance structure

The Kenward-Roger approximation will be used to estimate the denominator degrees of freedom.

The difference in mean change in the amyloid plaque level between treatment arms at 24, 52, and 76 weeks from baseline will be obtained through the least squares (LS) method. Its associated SE (standard error), 95% of confidence interval, and *p*-value derived from *t* test statistic will be reported as well.

The amyloid PET analysis described above will be based on the EES. A sensitivity PET analysis will be conducted using the per-protocol analysis set.

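### The primary ARIA-E model recuts baseline amyloid into sample terciles instead of the four centiloid bands used to stratify randomisation; this is a small inconsistency with no material effect on power.

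*SAP*

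**What the plan says.** Protocol section 6.3, under Randomization: "Participants will be stratified at baseline by amyloid PET scan results". The bands are 24.1 to <54, 54 to <79, 79 to <107 and >=107 centiloids. The second stratification factor is APOE genotype in three levels.

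Protocol section 9.3.2: "The logistic regression model will include the fixed effects for treatment, ApoE e4 status, and baseline amyloid level". It does not say how amyloid is coded.

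SAP section 4.3.2 lists treatment arm, APOE, microhemorrhage, superficial siderosis and amyloid as categorical effects. On APOE: "APOE e4 genotype status has 3 levels: heterozygous carrier, homozygous carrier, and non-carrier". On amyloid: "Baseline amyloid values are divided into terciles". It gives no cut-points, no analysis set in which the terciles are formed, and no reference level or centring.

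The version 2.0 entry in the SAP version history records the move to tertiles. Its rationale cell reads only: "In previous SAP, baseline PET in centiloids was a continuous covariate in the logistic regression model".

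Other SAP models use amyloid on the centiloid scale. In the PET mixed model (section 4.4.2), baseline amyloid and "baseline amyloid-by-time interaction are continuous effects". The ARIA-E prediction and biomarker models (sections 4.5.1 and 4.5.2) name baseline amyloid centiloid as a predictor. The sensitivity analyses in section 4.3.3 vary the risk-reduction margin and the intercept prior, but not the amyloid coding.

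**The concern.** One stratification factor is analysed as randomised and the other is not. When all four bands are occupied, two tercile cuts cannot reproduce three band boundaries, so the model's amyloid groups necessarily differ from the randomisation groups. The cut-points will be known only once the sample is in, whereas the bands were fixed in advance and are already recorded for every participant.

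An unexplained change of coding in the primary model, with no sensitivity analysis on that coding, leaves a reader unable to tell whether it matters. The same coding passes to the Week 52 and Week 76 ARIA-E models (section 4.4.1). It may also pass to the ARIA-H model (section 4.4.3), which describes its priors as built in a similar way but does not state its covariates. At stake are consistency with the design and full pre-specification, plus a small amount of precision.

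**Working it through.** **1. The plan's own power figure.** SAP section 5 reports 92.7% power with 720 completers (180 per arm), ARIA-E rates of 18.5% against 11.1%, and success if any of three arms has Pr(RD >= 0.2) > 0.8. A grid computation of the four-arm model without covariates (20,000 trials) gave 92.8%. That result takes the slope prior variance as 4, one intercept component as variance 4 and the other as precision 30.19. Reading both intercept components as precisions gives 91.6%. Reading every second argument as a variance gives 85.0%, and reading every one as a precision gives 73.6%. The SAP names slope priors only for the arms in this simulation, so 92.7% does not depend on how amyloid is coded. The first reading is used below.

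**2. Share of centiloid variance kept by each grouping.** Share = sum over groups of w_k (m_k - m)^2 / Var, where w_k is the group proportion, m_k the group mean and m the overall mean. The documents give no baseline amyloid distribution, so normal distributions truncated at 24.1 centiloids are assumed:

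| Mean/SD before truncation | Tercile cuts | Terciles keep | Four bands keep |
|---|---|---|---|
| 60/30 | 53.2, 76.2 | 81.3% | 89.5% |
| 80/35 | 68.4, 97.0 | 81.4% | 88.5% |
| 100/35 | 85.9, 115.6 | 80.8% | 82.0% |

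Terciles drop about 19%. The bands drop 10% to 18%, so they too discard information.

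**3. Effect on the primary analysis.** 720 participants were allocated in blocks within the 4 x 3 = 12 strata and analysed with APOE plus amyloid. There were 700 trials per setting, with every coding fitted to the same trials. Order below: terciles / bands / continuous.

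| Amyloid mean/SD; OR per SD | Power, % | Posterior SD of log RR |
|---|---|---|
| 80/35; 1.5 | 92.9 / 93.0 / 93.0 | 0.2388 / 0.2382 / 0.2387 |
| 80/35; 2.5 | 93.0 / 92.9 / 93.1 | 0.2386 / 0.2376 / 0.2367 |
| 60/30; 2.0 | 94.7 / 94.4 / 94.3 | 0.2397 / 0.2375 / 0.2381 |
| 100/35; 2.0 | 93.1 / 93.0 / 93.4 | 0.2379 / 0.2387 / 0.2370 |

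- Terciles to bands, power: +0.1, -0.1, -0.3 and -0.1 points.
- Terciles to continuous, power: +0.1, +0.1, -0.4 and +0.3 points.
- Terciles to bands, posterior SD: 0.2382/0.2388 - 1 = -0.25%, then -0.42%, -0.92% and +0.34%.
- Terciles to continuous, posterior SD: -0.04%, -0.80%, -0.67% and -0.38%.

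The Monte Carlo SE of each power is sqrt(0.93 x 0.07/700) = 0.0096, about 1 point.

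Under the null (80/35), the any-arm success rate was 7.3 / 7.3 / 7.6% at OR 1.5 and 8.0 / 8.4 / 9.4% at OR 2.5. The largest gap, 1.4 points, is for continuous amyloid and is not established with 700 trials. Across the settings in the table and the null, terciles and bands gave the same decision in 97.6% to 99.7% of trials.

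A second simulation of the same design, recording the mean SE of the log relative risk over ORs of 1.5 to 2.5 per SD, gave -0.7% to +0.4% for bands against terciles and -0.2% to -1.9% for continuous against terciles. At the most favourable end, 1/0.981^2 = 1.039, equivalent to about 4% more participants.

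**4. The intercept prior.** Its mean is the log odds of the historical rate: ln(0.185/0.815) = -1.48. With uncentred categorical covariates, the intercept is the log odds for a standard-arm participant in the reference level of every factor, which is generally not the overall rate. Its meaning therefore depends on the coding, which the SAP leaves open.

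**The case against.** The strongest reply is that nothing is broken. The protocol promises a baseline amyloid effect and the SAP supplies one. Neither document commits to modelling the bands, so they do not contradict each other. Tercile cutting is a stated rule that uses neither outcome nor arm, so not knowing the cut-points in advance opens no route to outcome-driven choice. No gain from the bands is detectable: terciles had nominally higher power in three of the four settings. If the complaint is lost information, the remedy is continuous centiloids rather than another grouping. The bands would also change the primary model again, and would alter what the intercept prior refers to.

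Most of this stands, and it rules out some tempting inferences. A reader might infer that departing from the strata invalidates the primary analysis or inflates its error rate. The documents do not support that, because both stratification factors are in the model and the null success rates for terciles and bands differ by no more than 0.4 points. A reader might also infer that the bands buy precision. They do not reliably: under the 100/35 assumption they keep 82.0% of the variance against 80.8%, and the posterior SD rises slightly.

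The intercept-prior objection does not favour terciles, because it applies equally to terciles with no stated reference level. What remains is that the design groups are fixed, known and already used for randomisation, and that the SAP gives no reason for its change.

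**Conclusion.** The point holds as a minor matter of design consistency and pre-specification. The primary model should carry amyloid in the groups used to randomise, as it already does for APOE, or the SAP should say why not. The primary conclusion is not at risk, and no material power gain is claimed for the bands. Continuous centiloids are what recover the discarded information, and the precision they return is also small.

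The sizes rest on assumptions that the documents do not supply: the amyloid distribution, an amyloid OR of 1.5 to 2.5 per SD, and an APOE mix of 30/52/18% (noncarrier, heterozygous, homozygous) with ORs 1, 1.8 and 4. In addition, the Bayesian simulation centred the covariates, left out microhemorrhage and siderosis, and used a Laplace approximation to the posterior. The absolute null success rates depend on these choices and on the reading of the priors. They serve here only to compare codings, and how they sit against the SAP's stated 5% is a separate question.

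**What to change.** - In SAP section 4.3.2, replace the tercile sentence with the four randomisation bands: 24.1 to <54, 54 to <79, 79 to <107 and >=107 centiloids.
- In the same section, state the reference level or centring for every categorical covariate, so that the intercept prior refers to a defined standard-arm rate.
- In section 4.3.3, add continuous centiloids, as in V1.0, as a pre-specified sensitivity analysis.
- Carry the same coding to the models in section 4.4.1, and to section 4.4.3 where that model follows 4.3.2.
- In the version history, give the reason for the V2.0 move away from continuous centiloids.

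The cost is a few sentences and a short model specification. The bands are already held from randomisation, and no new data are needed. The parameterisation needs some care because of the intercept prior. If Week 24 results have already been unblinded, keep the planned terciles as primary and report the bands and continuous centiloids as labelled sensitivity analyses.
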